12.7.2 Endometrial Thickness

Analysis of change in endometrial thickness from Baseline to Month 3 and Month 6 in the Treatment Period will be performed. The mean change from Baseline to Month 3 (TAU/TVU only) and Month 6 will be compared between each elagolix dose group and placebo using one-way ANOVA with treatment as the main effect.

In addition, the number and percentage of subjects with endometrial thickness of < 8 mm, ≥ 8 mm and ≤ 12 mm, > 12 mm and ≤ 18 mm, and > 18 mm in the Treatment and Post-Treatment Follow-up Periods will be summarized by treatment group at each relevant visit in the Treatment Period. No comparison will be made for the Post-Treatment Follow-up Period.

Change in endometrial thickness from Baseline to relevant Post-Treatment Follow-up visit(s) will be summarized by treatment group with descriptive statistics.

12.8 Columbia Suicide Severity Rating Scale (C-SSRS)

The C-SSRS data will be summarized as observed by treatment group. The C-SSRS – Baseline/Screening and C-SSRS – Since Last Visit questionnaires and corresponding scoring rules are presented in [Appendix L](#), [Appendix M](#) and [Appendix N](#).

The C-SSRS – Baseline/Screening measured at Day 1 will be considered as Baseline C-SSRS. Baseline C-SSRS will be summarized by treatment group. Other analysis of C-SSRS will only include subjects who have at least 1 post-baseline C-SSRS measurement, regardless of whether they had a baseline C-SSRS measurement. The number of subjects with suicidal ideation, suicidal behavior, and self-injurious behavior without suicidal intent at each scheduled assessment during Treatment Period will be summarized. In addition, this table will be repeated for providing a summary of lifetime

outcomes and past year outcomes at screening and Day 1. No statistical test will be performed.

The number of subjects with suicide-related treatment-emergent events based on the C-SSRS during Treatment Period will be summarized. No statistical test will be performed.

A listing of subjects with suicidal ideation, suicidal behavior, or self-injurious behavior without suicidal intent based on the C-SSRS during treatment period will be provided.

12.9 Pregnancy Results

Pregnancies and outcomes will be summarized by treatment group. Listings will be prepared of all pregnancy test results for any subject who ever had a positive pregnancy test at any time point during the study.

13.0 Summary of Changes from SAP Version 1.0

1. Spelled out abbreviations through the document for better clarity. Fixed grammar errors through the document.
2. Added definition of study end days; updated text and added more details in the definition of visit windows for non-bleeding endpoints for better clarity.
3. Updated the definition of Baseline for WPAI to consider only measurements collected on or before Study Day 1; updated the convention for handling multiple assessments in a specific time window for WPAI.
4. Added details on handling of AH data with character values.
5. Moved analysis for physician surgery questionnaire (PSQ) and reason for study participation questionnaire from Section 11.0 to Section 8.0 since the two questionnaires were only collected at baseline. Removed the summary for overall subjects for reason for study participation questionnaire.

6. Clarified the primary endpoint is the percentage of responders meeting two conditions, instead of a "composite" endpoint.
7. Clarified the steps in multiple imputation. Added details on pre-specified random seed for multiple imputation.
8. Added references for the multiple imputation procedures.
9. Updated the text on Mixed Model Repeated Measures (MMRM) for analysis of change or percent change from Baseline in MBL volume to each month for better clarity.
10. Added the summary of average number of days by bleeding intensity categories for two additional population: the subjects with > 0 bleeding/spotting days in Month 1; the subjects with 0 bleeding/spotting days in Month 1.
11. Updated the analysis for presence of adenomyosis in the Treatment and Post-Treatment Follow-up Period; defined Baseline presence of adenomyosis and the subset of subjects with adenomyosis identified at any point during the Baseline or Treatment Period; added summary of Baseline presence of adenomyosis; added efficacy analysis for subjects identified in the adenomyosis subset of interest.
12. Added details on analysis of post-treatment menses for better clarity. Added an additional population for analysis of time to first post-treatment menses and volume of bleeding in first post-treatment menses.
13. Added summary of any treatment-emergent AEs occurring in $\geq 5\%$ of subjects by system organ class (SOC) and preferred term (PT).
14. Updated the list of AEs of special interest in main text and in [Appendix Q](#).
15. Added summary and listing for subjects with sustained PCS vital sign value.
16. Added plots for both efficacy and safety analyses.

Appendix A. UFS-QoL

Pt. Initials: _____

Pt. ID: _____

Date: _____

UTERINE FIBROID SYMPTOM AND HEALTH-RELATED QUALITY OF LIFE QUESTIONNAIRE (UFS-QOL)

Listed below are symptoms experienced by women who have uterine fibroids. Please consider each symptom as it relates to your uterine fibroids or menstrual cycle. Each question asks how much distress you have experienced from each symptom during the previous 4 weeks.¹

There are no right or wrong answers. Please be sure to answer every question by checking (✓) the most appropriate box. If a question does not apply to you, please mark "not at all" as a response.

During the previous 4 weeks ¹ , how distressed were you by...	Not at all	A little bit	Some-what	A great deal	A very great deal
1. Heavy bleeding during your menstrual period					
2. Passing blood clots during your menstrual period					
3. Fluctuation in the duration of your menstrual period compared to your previous cycles					
4. Fluctuation in the length of your monthly cycle compared to your previous cycles					
5. Feeling tightness or pressure in your pelvic area					
6. Frequent urination during the daytime hours					
7. Frequent nighttime urination					
8. Feeling fatigued					

¹ This questionnaire has been modified by Abbott with the permission of the SIR Foundation. Specifically, rather than asking how much distress you have experienced from various symptoms during the past 3 months, this questionnaire focuses on the past 4 weeks. SIR Foundation has not tested and is not responsible for the validity of this modification. Abbott plans to test the validity of this instrument using phase 2a trial data. Your use of the questionnaire constitutes your agreement to release SIR Foundation from any responsibility for Abbott's changes to the document.

The following questions ask about your feelings and experiences regarding the impact of uterine fibroid symptoms on your life. Please consider each question as it relates to your experiences with uterine fibroids during the previous 4 weeks.¹

There are no right or wrong answers. Please be sure to answer every question by checking (✓) the most appropriate box. If the question does not apply to you, please check "none of the time" as your option.

During the previous 4 weeks ¹ , how often have your symptoms related to uterine fibroids...	None of the time	A little of the time	Some of the time	Most of the time	All of the time
9. Made you feel anxious about the unpredictable onset or duration of your periods?	 ₁	 ₂	 ₃	 ₄	 ₅
10. Made you anxious about traveling?	 ₁	 ₂	 ₃	 ₄	 ₅
11. Interfered with your physical activities?	 ₁	 ₂	 ₃	 ₄	 ₅
12. Caused you to feel tired or worn out?	 ₁	 ₂	 ₃	 ₄	 ₅
13. Made you decrease the amount of time you spent on exercise or other physical activities?	 ₁	 ₂	 ₃	 ₄	 ₅
14. Made you feel as if you are not in control of your life?	 ₁	 ₂	 ₃	 ₄	 ₅
15. Made you concerned about soiling underclothes?	 ₁	 ₂	 ₃	 ₄	 ₅
16. Made you feel less productive?	 ₁	 ₂	 ₃	 ₄	 ₅
17. Caused you to feel drowsy or sleepy during the day?	 ₁	 ₂	 ₃	 ₄	 ₅
18. Made you feel self-conscious of weight gain?	 ₁	 ₂	 ₃	 ₄	 ₅
19. Made you feel that it was difficult to carry out your usual activities?	 ₁	 ₂	 ₃	 ₄	 ₅
20. Interfered with your social activities?	 ₁	 ₂	 ₃	 ₄	 ₅
21. Made you feel conscious about the size and appearance of your stomach?	 ₁	 ₂	 ₃	 ₄	 ₅
22. Made you concerned about soiling bed linen?	 ₁	 ₂	 ₃	 ₄	 ₅

¹© Copyright 2001 Society of Interventional Radiology Foundation. All rights reserved
1\msk\h\z\abap\proj\p\1617\quest\orig\final\uls\sig.doc-2/12/2001

During the previous 4 weeks ¹ , how often have your symptoms related to uterine fibroids...	None of the time	A little of the time	Some of the time	Most of the time	All of the time
23. Made you feel sad, discouraged, or hopeless?					
24. Made you feel down hearted and blue?					
25. Made you feel wiped out?					
26. Caused you to be concerned or worried about your health?					
27. Caused you to plan activities more carefully?					
28. Made you feel inconvenienced about always carrying extra pads, tampons, and clothing to avoid accidents?					
29. Caused you embarrassment?					
30. Made you feel uncertain about your future?					
31. Made you feel irritable?					
32. Made you concerned about soiling outer clothes?					
33. Affected the size of clothing you wear during your periods?					
34. Made you feel that you are not in control of your health?					
35. Made you feel weak as if energy was drained from your body?					
36. Diminished your sexual desire?					
37. Caused you to avoid sexual relations?					

This questionnaire is being used at Abbott's independent election pursuant to a license from the SIR Foundation. Abbott is solely responsible for the administration of this questionnaire and any related findings, conclusions or recommendations arising from such use. SIR Foundation is not responsible for any such use, findings, conclusions, or recommendations.

Appendix B. UFS-QoL Scoring Manual

To calculate a symptom score for symptom severity, create a summed score from the items listed below and then use the formula below the table to transform the value. This will provide symptom scores where higher score values are indicative of greater symptom severity or bother and lower scores will indicate minimal symptom severity (high scores = bad).

Scale	Sum Item Values	Lowest and Highest Possible Raw Scores (Assuming All Related Scale Items are Answered)	Possible Raw Score Range (Assuming All Related Scale Items are Answered)
Symptom Severity	Sum 1 – 8	8, 40	32

Transformation for Symptom Severity Raw Score ONLY:

Transformed Score = (Actual raw score – lowest possible raw score)/possible raw score range × 100

For the UFS-QoL subscale (concern, activities, energy/mood, control, self-conscious, and sexual function), create summed scores of the items listed below for each individual subscale. To calculate the HRQL total score, sum the value of each individual subscale (do not sum individual items). Use the formula below to transform all values. Higher scores will be indicative of better UFS-QoL (high = good).

Scale	Sum Item Values	Lowest and Highest Possible Raw Scores (Assuming All Related Scale Items are Answered)	Possible Raw Score Range (Assuming All Related Scale Items are Answered)
Concern	9 + 15 + 22 + 28 + 32	5, 25	20
Activities	10 + 11 + 13 + 19 + 20 + 27 + 29	7, 35	28
Energy/Mood	12 + 17 + 23 + 24 + 25 + 31 + 35	7, 35	28
Control	14 + 16 + 26 + 30 + 34	5, 25	20
Self-conscious	18 + 21 + 33	3, 15	12
Sexual Function	36 + 37	2, 10	8
HRQL Total	Sum of 6 Subscale Scores	29, 145	116

Formula for transformation of UFS-QoL raw scores ONLY:

$$\text{Transformed Score} = (\text{Highest possible score} - \text{Actual raw score}) / \text{Possible raw score range} \times 100$$

HRQL total = Sum of 6 Subscale Scores.

Missing Items:

- For each subscale listed in the tables above, including the scale of Symptom Severity, if some of the answers for related scale items are missing (not to exceed 50% of the scale items, details refer to Missing Items rule 2 below), then the lowest possible raw score = $1 \times (\text{total number of related scale items answered})$ and the highest possible raw score = $5 \times (\text{total number of related scale items answered})$. And the possible raw score range = the highest possible raw score – the lowest possible raw score.
- For the subscale analyses, if $< 50\%$ of the scale items are missing, the scale should be retained with the mean scale score of the items present used to impute a score for the missing items. If $\geq 50\%$ of the items are missing, no scale score should be calculated, the subscale score should be considered missing. If a subscale score is missing, the HRQL total cannot be calculated.

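### The UFS-QoL scoring appendix gives two missing-item corrections without saying they are alternatives; using both mis-scores every partly answered scale

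*SAP*

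**What the plan says.** SAP section 11.3.6.1 analyses change from baseline in each UFS-QoL subscale and in the HRQL total by ANCOVA, each elagolix group against placebo. It refers missing scores to the scoring manual reproduced in Appendix B.

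The Missing Items part of Appendix B has two rules.

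- **Range adjustment.** It covers "For each subscale listed in the tables above, including the scale of Symptom Severity" and applies "if some of the answers for related scale items are missing". The lowest possible raw score becomes 1 times the number of items answered and the highest becomes 5 times that number. The range follows: "And the possible raw score range = the highest possible raw score – the lowest possible raw score". A parenthesis limits the rule: "not to exceed 50% of the scale items, details refer to Missing Items rule 2 below".
- **Mean imputation.** If fewer than half of a scale's items are missing, the scale is kept, with "the mean scale score of the items present used to impute a score for the missing items". At half or more missing, there is no score.

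For the HRQL total the instruction is "To calculate the HRQL total score, sum the value of each individual subscale (do not sum individual items"). The table gives it limits of 29 and 145 and a range of 116, under column headings that presume complete answers. No adjusted constants are given for the total.

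**The concern.** Both rules are triggered by the same event, a scale with some but fewer than half of its items missing, and each is a full correction on its own. Mean imputation restores the raw sum to the full number of items. The range adjustment lowers the limits to match a sum over the answered items only. Someone who programs the appendix line by line would set a full-length sum against shortened limits.

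The HRQL total has the opposite problem. If subscales are handled by range adjustment alone, their raw sums lack the missing items' points. Adding those sums and transforming with 145 and 116 treats each missing item as 0, which is below the lowest possible answer of 1.

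Two programmers could therefore derive different scores from the same questionnaire, and some would be wrong by several points. Both errors grow with the mean answer, so they need not cancel between arms even if items are missing equally often. They cancel in change from baseline only if the same shift occurs at both visits.

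**Working it through.** **Inputs (SAP Appendix B).** Items are scored 1 to 5. Symptom Severity has 8 items; Concern 5; Activities 7; Energy/Mood 7; Control 5; Self-conscious 3; Sexual Function 2. Symptom Severity is (raw − lowest)/range × 100, where high is bad. The HRQL subscales and total are (highest − raw)/range × 100, where high is good.

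**The plan's own figures.** The HRQL items number 5+7+7+5+3+2 = 29, so the limits are 29 and 5×29 = 145, with range 4×29 = 116. Symptom Severity gives 8, 40 and 32. All match the tables. They also show that the total is a sum of raw subscale scores.

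**Notation.** k items in the scale, m answered, mean answered value x.

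**One rule at a time, HRQL subscale.**
- Range adjustment only: (5m − mx)/(4m) = (5 − x)/4.
- Mean imputation only: (5k − kx)/(4k) = (5 − x)/4.

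These are identical. Symptom Severity gives (x − 1)/4 both ways.

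**Both rules together.** HRQL subscale: (5m − kx)/(4m). Symptom Severity: (kx − m)/(4m). Compared with the single-rule score, each moves towards worse by 25x(k − m)/m points.

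| Scale | k | m | x | One rule | Both rules |
|---|---|---|---|---|---|
| Symptom Severity | 8 | 7 | 3 | 50 | (24−7)/28 = 60.7 |
| Symptom Severity | 8 | 7 | 5 | 100 | (40−7)/28 = 117.9 |
| Activities | 7 | 6 | 3 | 50 | (30−21)/24 = 37.5 |
| Activities | 7 | 6 | 5 | 0 | (30−35)/24 = −20.8 |
| Concern or Control | 5 | 4 | 3 | 50 | (20−15)/16 = 31.25 |
| Self-conscious | 3 | 2 | 3 | 50 | (10−9)/8 = 12.5 |

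A score leaves 0-100 only when x > 5m/k. With one item missing, that is x above 4.375 (8 items), 4.286 (7), 4.0 (5) or 3.33 (3).

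**HRQL total, range adjustment only, constants 145 and 116 kept.** Each missing item raises the total by 100x/116.
- x = 3, complete: (145−87)/116 = 50.
- x = 3, 1 missing: (145−84)/116 = 52.6, a rise of 2.6.
- x = 3, 4 missing: (145−75)/116 = 60.3.
- Largest pattern allowed, 2+3+3+2+1+0 = 11 missing, with all other answers 1: (145−18)/116 = 109.5.

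**HRQL total with the limits also shrunk.** With M of the 29 items answered and equal answers throughout, (5M − Mx)/(4M) is correct. With unequal answers it still departs from imputation. Take one Self-conscious item missing, the other two at 5, and the remaining 26 items at 2. Imputation gives (145−67)/116 = 67.2, shrunk limits give (140−62)/112 = 69.6, and fixed constants without imputation give (145−62)/116 = 71.6.

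**The case against.** The best defence is that the appendix describes one method twice. The range adjustment mentions the imputation rule only inside a parenthesis about the 50% cut-off, which can be read as a pointer to the retention threshold and not as an order to correct again. The two rules give the same subscale scores, and if imputed items count as answered the range adjustment does nothing. This is a reasonable reading, but the text does not state it. The rules are listed one after the other, for the same scales and the same trigger.

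For the HRQL total, the constants 29, 145 and 116 stand under headings that presume complete data, so one may argue that they were never meant for partly answered forms. That is fair, and it makes the upward bias conditional: it needs range adjustment alone for the subscales and unchanged constants for the total. Keeping the constants is nonetheless the literal reading, because the range adjustment names subscales and Symptom Severity only.

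It is also true that the 117.9, −20.8 and 109.5 examples are extremes, that the questionnaire asks women to answer every question and offers a response for items that do not apply, and that the protocol and SAP place UFS-QoL outside the ranked endpoints. These points limit the importance of the error. They do not remove it: the 60.7 in place of 50 arises from middling answers and one skipped item, and a range check would not catch it.

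A reader might infer three stronger things. That scores will routinely fall outside 0-100: they do so only above the 5m/k threshold. That UFS-QoL scores are generally biased upward: using both rules biases towards worse, and only the HRQL total under the other reading is biased towards better. That the treatment comparison is biased: the documents give no item-missingness rate, overall or by arm, so this cannot be shown.

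**Conclusion.** The point holds as a defect in a prespecified scoring rule. If both corrections are applied as written, every partly answered scale is shifted towards worse by 25x(k − m)/m points, and scores can become impossible when answers are high. If only the range adjustment is applied and the total keeps 145 and 116, the HRQL total is too favourable by 100x/116 points per missing item. Complete questionnaires are unaffected.

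The per-scale sizes are exact arithmetic on Appendix B. The trial-level effect depends on how often items are skipped, which the documents do not say, and is probably modest. No primary or ranked result, alpha level or power figure depends on it. It should be corrected because the endpoint is tested between arms and the right rule is easy to state.

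**What to change.** In the Missing Items part of Appendix B, delete the range-adjustment rule, or state that it must not be combined with imputation. Then specify:

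1. When fewer than 50% of a scale's items are missing, replace each missing item by the mean of the answered items in that scale; otherwise the scale score is missing.
2. Transform with the full tabulated limits and range.
3. Build the HRQL total from the six imputed raw subscale scores, using 145 and 116.

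This gives the same subscale and Symptom Severity scores as the range adjustment used alone, and keeps every score within 0-100. Deleting the range adjustment also removes a small mismatch at exactly half missing, where one rule allows up to 50% and the other drops the scale at 50%.

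The cost is a few lines in Appendix B and a check of the scoring program. Data collection, tests and sample size do not change. The instrument developer's own manual is not among the documents, so the sponsor should confirm that the edited text agrees with it.

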Appendix C. Patient Global Impression of Change (PGIC-MB) – SAMPLE

Subjects will complete the PGIC-MB to assess the change in the severity of their menstrual bleeding (from very much improved to very much worse) since initiation of study drug by choosing one of seven responses at each scheduled monthly visit, starting with the Month 1 Visit in the Treatment Period or the Premature Discontinuation Visit, if applicable.

Visits to be completed: Treatment Period Month 1, Month 2, Month 3, Month 4, Month 5, Month 6/PD

Question:

Please answer the following question regarding your **menstrual bleeding**:

Since I started taking study medication, my **menstrual bleeding** has:

- Very much improved
- Much improved
- Minimally improved
- Not changed
- Minimally worse
- Much worse
- Very much worse

Appendix D. Patient Global Impression of Change, Non-Bleeding Uterine Fibroids Symptoms (PGIC-NBUFS) – SAMPLE

Subjects will complete the PGIC-NBUFS to document the presence of and to assess the change in the overall severity of non-bleeding symptoms and the severity of specific non-bleeding uterine fibroid symptoms (from very much improved to very much worse, or the subject will indicate whether she did not have a particular symptom or cannot remember if she had a particular symptom) at Treatment Period Month 1, Month 3 and Month 6, or the Premature Discontinuation Visit, if applicable.

Visits to be completed: Treatment Period Month 1, Month 3, Month 6/PD

Questions:

Please answer the following questions regarding your non-bleeding uterine fibroid symptoms, that is, any symptom(s) that is present, whether or not you are having your period:

1. Since I started taking study medication, my **abdominal or pelvic pain** has/is
 - Very much improved
 - Much improved
 - Minimally improved
 - Not changed
 - Minimally worse
 - Much worse
 - Very much worse

2. Since I started taking study medication, my **abdominal or pelvic pressure** has/is

- Very much improved
- Much improved
- Minimally improved
- Not changed
- Minimally worse
- Much worse
- Very much worse

3. Since I started taking study medication, my **abdominal or pelvic cramping** has/is

- Very much improved
- Much improved
- Minimally improved
- Not changed
- Minimally worse
- Much worse
- Very much worse

4. Since I started taking study medication, my **back pain** has/is

- Very much improved
- Much improved
- Minimally improved
- Not changed
- Minimally worse
- Much worse
- Very much worse

5. Since I started taking study medication, my **abdominal bloating** has/is
- Very much improved
 - Much improved
 - Minimally improved
 - Not changed
 - Minimally worse
 - Much worse
 - Very much worse
6. Since I started taking study medication, my **urinary problems (urinating too frequently or feeling a sudden need to urinate)** has/is
- Very much improved
 - Much improved
 - Minimally improved
 - Not changed
 - Minimally worse
 - Much worse
 - Very much worse
7. **Overall** since I started taking study medication, my **non-bleeding symptoms** have/are
- Very much improved
 - Much improved
 - Minimally improved
 - Not changed
 - Minimally worse
 - Much worse
 - Very much worse

